6.9 Diet/Activity/Other Considerations

6.9.1 Diet

Subjects should maintain a normal diet unless modifications are required to manage an AE such as diarrhea, nausea or vomiting.

6.9.2 Contraception

Pembrolizumab may have adverse effects on a fetus in utero. Furthermore, it is not known if pembrolizumab has transient adverse effects on the composition of sperm.

For this trial, male subjects will be considered to be of non-reproductive potential if they have azoospermia (whether due to having had a vasectomy or due to an underlying medical condition).

Female subjects will be considered of non-reproductive potential if they are either:

(1) postmenopausal (defined as at least 12 months with no menses without an alternative medical cause; in women <45 years of age a high follicle stimulating hormone (FSH) level in the postmenopausal range may be used to confirm a post-menopausal state in women not using hormonal contraception or hormonal replacement therapy. In the absence of 12 months of amenorrhea, a single FSH measurement is insufficient.);

OR

(2) have had a hysterectomy and/or bilateral oophorectomy, bilateral salpingectomy or bilateral tubal ligation/occlusion, at least 6 weeks prior to screening;

OR

(3) have a congenital or acquired condition that prevents childbearing.

Female and male subjects of reproductive potential must agree to avoid becoming pregnant or impregnating a partner, respectively, while receiving study drug and for 120 days after the last dose of study drug by complying with one of the following:

(1) practice abstinence[†] from heterosexual activity;

OR

(2) use (or have their partner use) acceptable contraception during heterosexual activity.

Acceptable methods of contraception are[‡]:

Single method (one of the following is acceptable):

- intrauterine device (IUD)
- vasectomy of a female subject's male partner
- contraceptive rod implanted into the skin

Combination method (requires use of two of the following):

- diaphragm with spermicide (cannot be used in conjunction with cervical cap/spermicide)
- cervical cap with spermicide (nulliparous women only)
- contraceptive sponge (nulliparous women only)
- male condom or female condom (cannot be used together)
- hormonal contraceptive: oral contraceptive pill (estrogen/progestin pill or progestin-only pill), contraceptive skin patch, vaginal contraceptive ring, or subcutaneous contraceptive injection

†Abstinence (relative to heterosexual activity) can be used as the sole method of contraception if it is consistently employed as the subject's preferred and usual lifestyle and if considered acceptable by local regulatory agencies and ERCs/IRBs. Periodic abstinence (e.g., calendar, ovulation, sympto-thermal, post-ovulation methods, etc.) and withdrawal are not acceptable methods of contraception.

‡If a contraceptive method listed above is restricted by local regulations/guidelines, then it does not qualify as an acceptable method of contraception for subjects participating at sites in this country/region.

Subjects should be informed that taking the study medication may involve unknown risks to the fetus (unborn baby) if pregnancy were to occur during the study. In order to participate in the study subjects of childbearing potential must adhere to the contraception requirement (described above) from the day of study medication initiation (or 14 days prior to the initiation of study medication for oral contraception) throughout the study period up to 120 days after the last dose of trial therapy. If there is any question that a subject of childbearing potential will not reliably comply with the requirements for contraception, that subject should not be entered into the study.

6.9.3 Use in Pregnancy

If a subject inadvertently becomes pregnant while on treatment with pembrolizumab, the subject will immediately be removed from the study. The site will contact the subject at least monthly and document the subject's status until the pregnancy has been completed or terminated. The outcome of the pregnancy will be reported to the Sponsor and to Merck without delay and within 24 hours to the Sponsor and within 2 working days to Merck if the outcome is a serious adverse experience (e.g., death, abortion, congenital anomaly, or other disabling or life-threatening complication to the mother or newborn).

The study investigator will make every effort to obtain permission to follow the outcome of the pregnancy and report the condition of the fetus or newborn to the Sponsor. If a male subject impregnates his female partner the study personnel at the site must be informed immediately and the pregnancy reported to the Sponsor and to Merck and followed as described above.

6.9.4 Use in Nursing Women

It is unknown whether pembrolizumab is excreted in human milk. Since many drugs are excreted in human milk, and because of the potential for serious adverse reactions in the nursing infant, subjects who are breast-feeding are not eligible for enrollment.

7.0 SUBJECT WITHDRAWAL/DISCONTINUATION CRITERIA

Subjects may withdraw consent at any time for any reason or be dropped from the trial at the discretion of the investigator should any untoward effect occur. In addition, a subject may be withdrawn by the investigator or the Sponsor if enrollment into the trial is inappropriate, the trial plan is violated, or for administrative and/or other safety reasons.

A subject must be discontinued from the trial for any of the following reasons:

- The subject or legal representative (such as a parent or legal guardian) withdraws consent.
- Confirmed radiographic disease progression
- Unacceptable adverse experiences
- Intercurrent illness that prevents further administration of treatment
- Investigator's decision to withdraw the subject
- The subject has a confirmed positive serum pregnancy test
- Noncompliance with trial treatment or procedure requirements
- The subject is lost to follow-up
- Completed 24 months of uninterrupted treatment with pembrolizumab or 35 administrations of study medication, whichever is later.
- Administrative reasons

The End of Treatment and Follow-up visit procedures are listed in Section 8 (Protocol Flow Chart) and Section 10.0.1 (Visit Requirements). After the end of treatment, each subject will be followed for 30 days for adverse event monitoring (serious adverse events will be collected for 90 days after the end of treatment). Subjects who discontinue for reasons other than progressive disease will have post-treatment follow-up for disease status until disease progression, initiating a non-study cancer treatment, withdrawing consent or becoming lost to follow-up. After documented disease progression each subject will be followed by telephone for overall survival until death, withdrawal of consent, or the end of the study, whichever occurs first.

7.1 Discontinuation of Study Therapy after CR

Discontinuation of treatment may be considered for subjects who have attained a confirmed CR that have been treated for at least 24 weeks with pembrolizumab and had at least two treatments with pembrolizumab beyond the date when the initial CR was declared.

7.2 Subject Replacement Strategy

We anticipate enrollment of 39 patients for which tumor and toxicity assessments following pembrolizumab administration can be made. We will replace patients enrolled for which clinical trial discontinuation was performed prior to any administration of pembrolizumab or those for which pembrolizumab is discontinued due to acute hypersensitivity reactions during the first administration of pembrolizumab. An attempt will be made to assess tumor response in all enrolled patients as specified in the protocol. However, patients experiencing clinical deterioration after two doses of pembrolizumab, will be considered treatment failures and will count as tumor progression. These patients will not be replaced.

We are also expecting that 30% of the patients enrolled will be negative on the FATS1 assay, which will be conducted in batched analyses.

See section 6.1.1 and 12.0.1 for expansion cohort.

7.3 Clinical Criteria for Early Trial Termination

Early trial termination will be the result of the criteria specified below. In the event of Merck decision to no longer supply study drug, ample notification will be provided so that appropriate adjustments to subject treatment can be made.

1. Quality or quantity of data recording is inaccurate or incomplete
2. Poor adherence to protocol and regulatory requirements
3. Incidence or severity of new adverse pembrolizumab drug reaction as reported by MERCK to the FDA indicates a potential health hazard to subjects and lead to modification in the drug labeling. The trial could be re-open following the adoption of required modifications in administration.

8 TRIAL FLOW CHART

8.1 Table 6. Study Flow Chart

Trial Period:	Screening	Treatment Cycles								End of Treatment	Post-Treatment			
		Main Study Screening	1	2	3	4	To be repeated beyond 8 cycles				Discon	Safety Follow-up	Follow Up Visits ^b	Survival Follow-Up
Treatment Cycle/Title:							5	6	7	8				
Scheduling Window (Days):	-21 to -1			± 3	± 3	± 3	± 3	± 3	± 3	± 3	At time of Discon	30 days post discon	Every 8 weeks post discon	Every 12 weeks
Informed Consent	X													
Inclusion/Exclusion Criteria	X													
Demographics and Medical History	X	X	X	X	X	X	X	X	X	X				
Prior and Concomitant Medication Review	X	X	X	X	X	X	X	X	X	X				
Trial Treatment Administration		X	X	X	X	X	X	X	X	X				
Post-study anticancer therapy status												X	X	
Survival Status												X	X	X
Review Adverse Events		X	X	X	X	X	X	X	X	X				
Full Physical Examination	X													
Directed Physical Examination		X	X	X	X	X	X	X	X	X				
Vital Signs and Weight	X	X	X	X	X	X	X	X	X	X				
ECOG Performance Status	X	X	X	X	X	X	X	X	X	X				
Pregnancy Test – Urine or Serum β-HCG	X ^c													
PT/INR and aPTT	X ^a													
CBC with Differential	X ^a	X ^b	X	X	X	X	X	X	X	X				
Comprehensive Serum Chemistry Panel (see Table 9 for lab details)	X ^a	X ^b	X	X	X	X	X	X	X	X				
Urinalysis	X ^a													
T3, FT4 and TSH	X ^a			X			X							

Efficacy Measurements											
Tumor Imaging	X			X			X ^d		X		
Archival Tissue Collection/Correlative Studies Blood											
Archival or Newly Obtained Tissue Collection	X										
Correlative Studies Blood Collection See Protocol Lab Manual.	X	X	X	X					X		

^a Must be performed within 10 days of the first treatment visit (Cycle 1 Day 1).

^b Hematology (CBC with differential) and Creatinine results must be available and reviewed by the Investigator prior to infusion. A spot creatinine result may be used to proceed with treatment, as Chemistry results may not be available.

^c Must be performed within 72 hours of the first treatment visit (Cycle 1 Day 1).

^d **Tumor imaging will only be required every 12 weeks for patients that have been on treatment for more than 1 year.**

9.0 TRIAL PROCEDURES

The Trial Flow Chart - Section 8.0 summarizes the trial procedures to be performed at each visit. Individual trial procedures are described in detail below. It may be necessary to perform these procedures at unscheduled time points if deemed clinically necessary by the investigator.

Furthermore, additional evaluations/testing may be deemed necessary by the Sponsor and/or Merck for reasons related to subject safety. In some cases, such evaluation/testing may be potentially sensitive in nature (e.g., HIV, Hepatitis C, etc.), and thus local regulations may require that additional informed consent be obtained from the subject. In these cases, such evaluations/testing will be performed in accordance with those regulations.

9.0.1 Administrative Procedures

9.0.1.1 Informed Consent

The Investigator must obtain documented consent from each potential subject prior to participating in a clinical trial.

Consent must be documented by the subject's dated signature or by the subject's legally acceptable representative's dated signature on a consent form along with the dated signature of the person conducting the consent discussion.

A copy of the signed and dated consent form should be given to the subject before participation in the trial.

The initial informed consent form, any subsequent revised written informed consent form and any written information provided to the subject must receive the IRB/ERC's approval/favorable opinion in advance of use. The subject or his/her legally acceptable representative should be informed in a timely manner if new information becomes available that may be relevant to the subject's willingness to continue participation in the trial. The communication of this information will be provided and documented via a revised consent form or addendum to the original consent form that captures the subject's dated signature or by the subject's legally acceptable representative's dated signature.

Specifics about a trial and the trial population will be added to the consent form template at the protocol level.

The informed consent will adhere to IRB/ERC requirements, applicable laws and regulations and Sponsor requirements.

9.0.1.2 Inclusion/Exclusion Criteria

All inclusion and exclusion criteria will be reviewed by the investigator or qualified designee to ensure that the subject qualifies for the trial.

9.0.1.3 Medical History

A medical history will be obtained by the investigator or qualified designee. Medical history will include all active conditions, and any condition diagnosed within the prior 10 years that are considered to be clinically significant by the Investigator. Details regarding the disease for

which the subject has enrolled in this study will be recorded separately and not listed as medical history.

9.0.1.4 Prior and Concomitant Medications Review

9.0.1.4.1 Prior Medications

The investigator or qualified designee will review prior medication use, including any protocol-specified washout requirement, and record prior medication taken by the subject within 21 days before starting the trial. Treatment for the disease for which the subject has enrolled in this study will be recorded separately and not listed as a prior medication.

9.0.1.4.2 Concomitant Medications

The investigator or qualified designee will record medication, if any, taken by the subject during the trial. All medications related to reportable SAEs and ECIs should be recorded as defined in Section 9.2.

9.0.1.5 Disease Details and Treatments

9.0.1.5.1 Disease Details

The investigator or qualified designee will obtain prior and current details regarding disease status.

9.0.1.5.2 Prior Treatment Details

The investigator or qualified designee will review all prior cancer treatments including systemic treatments, radiation and surgeries.

9.0.1.5.3 Subsequent Anti-Cancer Therapy Status

The investigator or qualified designee will review all new anti-neoplastic therapy initiated after the last dose of trial treatment. If a subject initiates a new anti-cancer therapy within 30 days after the last dose of trial treatment, the 30 day Safety Follow-up visit must occur before the first dose of the new therapy. Once new anti-cancer therapy has been initiated the subject will move into survival follow-up.

9.0.2 Clinical Procedures/Assessments

9.0.2.1 Adverse Event (AE) Monitoring

The investigator or qualified designee will assess each subject to evaluate for potential new or worsening AEs as specified in the Trial Flow Chart and more frequently if clinically indicated. Adverse experiences will be graded and recorded throughout the study and during the follow-up period according to NCI CTCAE Version 4.0 (see Section 11.2). Toxicities will be characterized in terms regarding seriousness, causality, toxicity grading, and action taken with regard to trial treatment.

9.0.2.2 Full Physical Exam

The investigator or qualified designee will perform a complete physical exam during the screening period. Clinically significant abnormal findings should be recorded as medical history. A full physical exam should be performed during screening,

9.0.2.3 Directed Physical Exam

For cycles that do not require a full physical exam per the Trial Flow Chart, the investigator or qualified designee will perform a directed physical exam as clinically indicated prior to trial treatment administration.

9.0.2.4 Vital Signs

The investigator or qualified designee will take vital signs at screening, prior to the administration of each dose of trial treatment and at treatment discontinuation as specified in the Trial Flow Chart (Section 8). Vital signs should include temperature, pulse, respiratory rate, weight and blood pressure. Height will be measured at screening only.

9.0.2.5 Eastern Cooperative Oncology Group (ECOG) Performance Scale

The investigator or qualified designee will assess ECOG status (see below) at screening, prior to the administration of each dose of trial treatment and discontinuation of trial treatment as specified in the Trial Flow Chart.

9.0.2.6 Tumor Imaging and Assessment of Disease

Tumor assessments will be performed by computer tomography (CT) or Magnetic Resonance Imaging (MRI). Measurable disease will be required by computer tomography or MRI examination obtained within 21 days of first dose of therapy. Scans obtained prior to consenting will be allowed, as long as performed within 21 days of study initiation. CT Scans or MRI's will be repeated every 2 cycles (3 weeks cycles); that is before every third dose of pembrolizumab in order to assess response to therapy. [Tumor imaging will only be required every 12 weeks for patients that have been on treatment for more than 1 year.](#) Immune-related Response Criteria (irRC) [30] will be utilized for assessment of response to therapy.

Systematic criteria designated immune-related response criteria were defined based on four distinct response patterns seen after administration of ipilimumab: (a) shrinkage in baseline lesions, without new lesions; (b) durable stable disease (in some patients followed by a slow, steady decline in total tumor burden); (c) response after an increase in total tumor burden; and (d) response in the presence of new lesions. These four patterns were associated with favorable survival [30].

For the irRC index and measurable new lesions are taken into account to calculate evolving tumor burden. At baseline, the sum of the products of the two largest perpendicular diameters (SPD) of all index lesions (five lesions per organ, up to 10 visceral lesions) is calculated. At each subsequent tumor assessment, the SPD of the index lesions and of new, measurable lesions (up to 5 new lesions per organ; 10 visceral lesions) are added together to provide the total tumor burden. A comparison of the use of SPD in WHO criteria versus the use of tumor burden in irRC is presented in Table 8.

Table 7. Comparison between WHO criteria and the irRC

WHO		irRC
New, measurable lesions	Always represent PD	Incorporated into tumor burden.
New, nonmeasurable lesions	Always represent PD	Do not define progression (but preclude irCR)

Non-index lesions	Changes contribute to defining best overall response	Contribute to defining irCR (complete disappearance required)
CR	Disappearance of all lesions in two consecutive observations not less than 4 weeks apart.	Disappearance of all lesions in two consecutive observations not less than 4 weeks apart.
PR	$\geq 50\%$ decrease in SPD compared with baseline in two observations at least 4 weeks apart, in absence of new lesions or unequivocal progression of non-index lesions.	$\geq 50\%$ decrease in tumor burden compared with baseline in two observations at least 4 weeks apart.
SD	50% decrease in SPD compared to baseline cannot be established nor 25% increase compared with nadir, in absence of new lesions or unequivocal progression of non-index lesions.	50% decrease in tumor burden compared with baseline cannot be established nor 25% increase compared with nadir.
PD	At least 25% increase in SPD compared with nadir and/or unequivocal progression of non-index lesions and/or appearance of new lesions (at any single time point).	At least 25% increase in tumor burden compared with nadir (at any single time point) in two consecutive observations at least 4 weeks apart.

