2.0 TRIAL DESIGN

Phase II trial in which patients with metastatic solid tumors experiencing progression after first line standard chemotherapy or for which there is no standard chemotherapy, and for which pembrolizumab does not have an FDA or compendia listing approved indication, will receive pembrolizumab intravenously at a dose of 200 mg every 3 weeks.

The end points are the immune-related objective response rate (primary) and the 20-week immune-related progression-free survival rate (secondary). Availability of paraffin embedded tumor material and willingness to provide blood for plasma DNA mutational analysis will be required for enrollment, as well as standard acceptable organ function and no history of autoimmune disease or previous treatment with immune check-point inhibitors. CT assessment at baseline and after every 8 weeks will be obtained to measure immune-related objective response rates. Patients will continue treatment until tumor progression or intolerable toxicity.

Stratification based on FANCD2 foci formation in tumor material (see below) to evaluate potential differences in activity will be performed. Exploratory correlatives include evaluation of mutation load on tumor and cell free DNA analysis and of gut microbiome composition on fecal samples.

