6.4 Dose Selection/Modification

Dose Selection

The rationale for selection of doses to be used in this trial is provided in Section 4.0 – Background and Rationale. Details on preparation and administration of pembrolizumab (MK-3475) are provided in the Package Insert.

Dose Modification (Escalation/Titration/Other)

Adverse events (both non-serious and serious) associated with pembrolizumab exposure may represent an immunologic etiology. These adverse events may occur shortly after the first dose or several months after the last dose of treatment. Pembrolizumab must be withheld for drug-related toxicities and severe or life-threatening AEs as per Table 4 below. See Section 6.8.1 for supportive care guidelines, including use of corticosteroids.

Table 4. Dose Modification and Toxicity Management Guidelines for Immune-related AEs Associated with Pembrolizumab

General instructions:

1. Corticosteroid taper should be initiated upon AE improving to Grade 1 or less and continue to taper over at least 4 weeks.
2. For situations where pembrolizumab has been withheld, pembrolizumab can be resumed after AE has been reduced to Grade 1 or 0 and corticosteroid has been tapered. Pembrolizumab should be permanently discontinued if AE does not resolve within 12 weeks of last dose or corticosteroids cannot be reduced to ≤ 10 mg prednisone or equivalent per day within 12 weeks.
3. For severe and life-threatening irAEs, IV corticosteroid should be initiated first followed by oral steroid. Other immunosuppressive treatment should be initiated if irAEs cannot be controlled by corticosteroids.

Immune-related AEs	Toxicity grade or conditions (CTCAEv4.0)	Action taken to pembrolizumab	irAE management with corticosteroid and/or other therapies	Monitor and follow-up
Pneumonitis	Grade 2	Withhold	
 Administer corticosteroids (initial dose of 1-2 mg/kg prednisone or equivalent) followed by taper 	
 Monitor participants for signs and symptoms of pneumonitis Evaluate participants with suspected pneumonitis with radiographic imaging and initiate corticosteroid treatment Add prophylactic antibiotics for opportunistic infections
	Grade 3 or 4, or recurrent Grade 2	Permanently discontinue		

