6.5 Timing of Dose Administration

Trial treatment should be administered on Day 1 of each cycle after all procedures/assessments have been completed as detailed on the Trial Flow Chart (Section 8.0). Trial treatment may be administered up to 3 days before or after the scheduled Day 1 of each cycle due to administrative reasons.

All trial treatments will be administered on an outpatient basis.

Pembrolizumab 200 mg will be administered as a 30 minute IV infusion every 3 weeks. Sites should make every effort to target infusion timing to be as close to 30 minutes as possible. However, given the variability of infusion pumps from site to site, a window of -5 minutes and +10 minutes is permitted (i.e., infusion time is 30 minutes: -5 min/+10 min).

The Package Insert contains specific instructions for the preparation of the pembrolizumab infusion fluid and administration of infusion solution.

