10.0.1.1 Follow-up Visits

Subjects who discontinue trial treatment for a reason other than disease progression will move into the Follow-Up Phase and should be assessed every 6 weeks (42 ± 7 days) by radiologic imaging to monitor disease status. After 1 year, the imaging time point will occur every 9 weeks (± 7 days). Every effort should be made to collect information regarding disease status until the start of new anti-neoplastic therapy, disease progression, death, or end of the study. Information regarding post-study anti-neoplastic treatment will be collected if new treatment is initiated.

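### Section 9.0.2.6 times on-treatment scans by dose count and Section 2.0 by calendar; if the dose count governs, a toxicity hold can also postpone the scan and date progression late for the 20-week irPFS.

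*Combined protocol and SAP*

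**What the plan says.** Three parts of the protocol set imaging times.

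- **On treatment, by dose count.** Section 9.0.2.6: "CT Scans or MRI's will be repeated every 2 cycles (3 weeks cycles); that is before every third dose of pembrolizumab". Section 6.5 ties the cycle to the dose ("Trial treatment should be administered on Day 1 of each cycle") and sets the interval ("Pembrolizumab 200 mg will be administered as a 30 minute IV infusion every 3 weeks").
- **On treatment, by calendar.** Section 2.0: "CT assessment at baseline and after every 8 weeks will be obtained to measure immune-related objective response rates".
- **After treatment is discontinued for a reason other than progression, by calendar.** Section 10.0.1.1: patients "should be assessed every 6 weeks (42 ± 7 days) by radiologic imaging to monitor disease status".

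Table 4 in Section 6.4 lets drug be withheld for toxicity. Treatment may restart on this condition: "pembrolizumab can be resumed after AE has been reduced to Grade 1 or 0 and corticosteroid has been tapered". The outer limit is: "Pembrolizumab should be permanently discontinued if AE does not resolve within 12 weeks of last dose". No imaging instruction is attached to a hold.

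Section 12 estimates irPFS by Kaplan-Meier and reports the 20-week value for comparison with the literature. It does not say how progression is dated or how a missed or late scan is handled.

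**The concern.** A patient on hold has not discontinued, so the follow-up imaging of Section 10.0.1.1 does not apply. If the on-treatment scan waits for the next dose, the held patient is scanned less often than a patient who continues and less often than one who stops. How often progression is looked for would then depend on toxicity.

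Progression that arises silently during a hold would be dated at the first scan after it. If that scan falls after week 20, the patient appears progression-free at 20 weeks. The error runs in one direction, upward. If holds were more frequent in one FATSI group, it would also blur the irPFS comparison between groups.

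**Working it through.** **The plan's own figures.** The documents give no figure for a scan gap. The nearest stated figures are the two-stage characteristics in Table 10 (continue with at least 2 responses in 20, reject with at least 4 in 39). They reproduce:

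- Early termination under 5%: 0.95^20 + 20 × 0.05 × 0.95^19 = 0.358 + 0.377 = 0.736 (stated 0.74).
- Type I error, summing P(X1 = x) × P(X2 ≥ 4 − x) over x ≥ 2 with 20 and 19 patients: 0.099 (stated 0.099).
- Power at 20%, same sum: 0.917 (stated 91.7%).
- Expected size: 20 + 19 × (1 − 0.736) = 25.0 (stated 25).

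None of these uses the timing of scans, so the point does not touch them.

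**Scan calendar if 9.0.2.6 governs and a hold postpones the cycle.** Dose 1 is at week 0 and doses are 3 weeks apart. Scans every 2 cycles fall before doses 3, 5 and 7, at weeks 6, 12 and 18. Let w be the interval in weeks between the last dose before the hold and the next dose.

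| Hold after dose | w = 6 | w = 9 | w = 12 |
|---|---|---|---|
| 3 or 4 | scans 6, 15 (gap 9) | scans 6, 18 (gap 12) | scans 6, 21 (gap 15) |
| 5 or 6 | scans 12, 21 (gap 9) | scans 12, 24 (gap 12) | scans 12, 27 (gap 15) |

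Worked case: doses at weeks 0, 3, 6 and 9, then a hold to the limit. Dose 5 and its scan fall at 9 + 12 = week 21, and the scans otherwise due at weeks 12 and 18 are not triggered.

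When does the week-6 scan become the last one before week 20?

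- Hold after dose 4: dose 5 is at 9 + w, and 9 + w > 20 needs w > 11.
- Hold after dose 3: dose 5 is at 6 + w + 3, which also needs w > 11.

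Holds after dose 5 or 6 push the week-18 scan past week 20 more easily, but the last scan is then week 12.

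Reading every third dose literally as doses 3, 6 and 9 would give weeks 6 to 24 (18 weeks) in the worked case, but that does not agree with every 2 cycles.

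**Scan calendar if Section 2.0 governs.** Scans fall at weeks 8, 16 and 24 whatever happens to dosing. The week 6 to 21 gap does not arise.

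**Effect on 20-week irPFS.** With no censoring, one patient wrongly counted as progression-free moves the estimate by 1/39 = 2.6 points, or 1/12 = 8.3 points among the 12 expected FATSI-negative patients.

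For the expected shift, assume:

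- true 20-week irPFS of p, with equal risk at the scans of weeks 6, 12 and 18;
- a patient progression-free at week 6 and held over weeks 9 to 21;
- progression that is all clinically silent and dated at the scan where it is first seen.

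The probability that the hold hides an event is 1 − p^(2/3). Section 4.4 reports irPFS rates from 11% to 78% in the published pembrolizumab study of mismatch repair. It does not restate the time point there, so using them as 20-week rates is an assumption.

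- p = 0.78: 1 − 0.847 = 0.153, and 0.153/39 = 0.4 points.
- p = 0.11: 1 − 0.230 = 0.770, and 0.770/39 = 2.0 points.

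**If irPD is dated at confirmation.** Section 9.0.2.7 requires a second scan at least 4 weeks later. Progression first seen at week 18 is then confirmed at week 22 or later even without a hold, so only week-12 events are hidden. The shift is (1 − p^(1/3))/39: 0.079/39 = 0.2 points at 78% and 0.521/39 = 1.3 points at 11%.

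**The case against.** The best answer is Section 2.0. Its calendar wording would have the example patient scanned at weeks 8 and 16. It differs from 9.0.2.6 in the anchor as well as the interval, so the two cannot be treated as one rule with a disputed length. This stands: the gap is conditional on 9.0.2.6 governing.

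Nor do the documents say that a withheld dose stops the cycle count. Section 6.5 refers to a scheduled Day 1, and a held dose could be treated as skipped while cycles run on. The flow chart sets imaging out by cycle but does not settle this. This stands too.

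The week-21 case needs an interval above 11 weeks against a limit of 12, so it is an extreme. Interruptions unrelated to toxicity add little, since Section 6.4 asks for a return within 3 weeks unless discussed with the sponsor. Section 7.2 counts clinical deterioration after two doses as progression, and Section 9.0 allows unscheduled procedures. Only progression missed by both is affected, so the shifts above are upper values for each p.

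A reader might infer that the plan leaves held patients unscanned from week 6 to week 21 and counts them as progression-free. The documents do not support that as a flat statement. The gap depends on the reading of two sections, and the counting follows from the lack of a dating rule, not from a stated one. A reader might also infer that the stage 1 response count is compromised. Section 12 sets no deadline for those responses, so a late scan delays a response and does not by itself remove it.

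What the objection does not answer is that no section requires a scan during a hold or says whether scans move with doses.

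**Conclusion.** The point holds in a conditional form. Sections 2.0 and 9.0.2.6 disagree on how on-treatment scans are anchored. If the dose-count rule governs and holds postpone the cycle, assessment timing depends on toxicity. Holds that lengthen the interval after dose 3 or 4 to 6 or 9 weeks delay the dating of progression; only a hold near the 12-week limit leaves weeks 6 to 21 without a required scan.

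The consequence is a possible upward shift in a secondary, uncontrolled estimate. The expected size is 0.4 to 2.0 points per patient held over weeks 9 to 21, or 0.2 to 1.3 if irPD is dated at confirmation, and less where progression shows clinically. The total cannot be given because the documents do not state how many such holds to expect. The primary response design keeps its operating characteristics. This is a cheap improvement worth making, not a flaw that threatens the trial's main conclusion.

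**What to change.** 1. Reconcile Sections 2.0 and 9.0.2.6 so that one on-treatment imaging interval applies. The choice of interval is the sponsor's, and the rest of the fix works with either.
2. In Section 9.0.2.6 and the flow chart, anchor on-treatment scans to calendar weeks from Cycle 1 Day 1, with the ±7-day window already used in Section 10.0.1.1.
3. State that scans do not move when a dose is delayed, withheld or skipped.

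With scans fixed in this way, the example patient is scanned at weeks 6, 12 and 18 or at weeks 8 and 16. The last scan before week 20 is then week 18 or 16 instead of week 6, and the longest nominal gap is 6 or 8 weeks instead of 15.

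The cost is protocol wording. The scans for held patients are those already due by calendar. The downside is that a held patient may need a scan visit separate from a dosing visit. No dosing or toxicity rule changes.
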